# 9.2 Discontinuation of trial intervention and loss of follow-up

Each participant has the right to withdraw from any aspect of the trial at any time. The participant's care will not be affected at any time by declining to participate or withdrawing from the trial. A clear distinction must be made as to what aspect of the trial the participant is discontinuing from, for example:

- Discontinue from the entire trial and do not want any data or samples already collected relating to them to be used
- Discontinue from the trial, study product and all subsequent trial follow-up (sample collection and data collection), but data and samples already obtained up to this point can be used
- Discontinue from study product and all subsequent sample and questionnaire data collection, but happy for routine medical and dental data to be collected.

The reason for participant withdrawal will be detailed in a Case Report Form (CRF) and reviewed by the CI and independent committee. Any queries relating to the potential withdrawal of a participant should be forwarded to the coordinating centre immediately.

Apart from the participant's individual choice to withdraw from the study, the trial intervention will be terminated if the participant

- Tests positive for CV-19
- Prolonged hospitalisation for any medical or surgical reasons not otherwise diagnosed at the time of recruitment
- Experiences in unexpected series of adverse reactions to the study product

‡NB All data collected prior to withdrawal will not be deleted and will be included in the analysis on the condition that appropriate consent is in place. Routinely collected health data will still be obtained for use in the study unless the participant explicitly states otherwise.

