#### **Serious Adverse Events:**

# **SAR** reporting

SAEs will be reported by the RN on the ELDER Monthly Record

Where an adverse event meets the definition of a SAR the Clinical Trial Coordinator should be informed immediately, and a SAR form should be completed by the responsible person and emailed to the ELDER Trial email address (See section 10.5 for more details).

Email: [contact] [contact]

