# 8. Trial Intervention

The consented care homes will be assigned randomly to one of the study arms: - (a) Group 1: non-supplemented milk (placebo), (b) Group 2: milk supplemented with fluoride (5.0 mg F/l), (c) Group 3: milk supplemented with probiotics (Lactobacillus), and (d) Group 4: milk supplemented with fluoride and probiotics. All subjects will be asked to drink a glass of plain/supplemented milk once daily, five days a week, for nine months. Fluoridated milk or probiotics, or placebo (referred to as the Study product) will be administered by the resident's routine caregiver during medicinal/meal rounds. The study product will be sourced from the manufacturer and transported to the study site. Fluoridated milk will be distributed in a small carton, and the probiotics will be provided as a powder in sealed sachets. The preferred route of administration is as follows:

1. The carton containing fluoridated milk is to be emptied into a tall glass and then consumed.

2. The probiotic powder is to be dispensed in a spoon, then added to a prepared glass of skimmed milk/fluoridated milk, mixed well and then consumed

Each care home will be provided with the manufacturer's dossier detailing the composition of the probiotic form and fluoridated milk. After allocation, probiotic sachets will be distributed to the care home at the beginning of the trial, whereas milk (both skimmed & fluoridated) will be distributed to the trial sites weekly. Participants admitted to the hospital would not be expected to continue taking the study product during their hospital stay.

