# Serious Adverse Event (SAE)

In research other than CTIMPS, an SAE is any adverse event that a) Results in death; (b) Is life-threatening\*; (c) Requires hospitalisation or prolongation of existing hospitalisation; (d) Results in persistent or significant disability or incapacity; (e) Consists of a congenital anomaly or birth defect or (f) Is otherwise considered medically significant by the investigator. [The Medicine for Human Use (Clinical Trials) Regulations (2004) as amended; and the Dir 2001/20/EC Art 2(o)]

\*Life-threatening in this context refers to a reaction in which the patient was at risk of death at the time of the reaction; it does not refer to a reaction that hypothetically might have caused death if more severe (ICH-E2D Guideline).

An SAE occurring to a research participant should be reported to the REC where in the opinion of the CI, the event was:

- ➤ Related that is, it resulted from the administration of any of the research procedures, and
- ➤ Unexpected that is, the type of event is not listed in the protocol as an expected occurrence.

Therefore, the relatedness or unexpectedness of an event will be reviewed by the CI at each site and wherein the opinion of the CI, the SAE will be classed appropriately and reported to the main REC. For ease of recording and reporting, in this study, an SAE thought to be probably or certainly related to the study product will be referred to as a Serious Adverse Reaction (SAR).

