#### 10.5.3 Serious Adverse Reaction

An SAE classified by the delivery staff/CTC and further confirmed by the CI as being probably or definitely related to the study product (diagnostic tests confirming septicaemia or the suspected pathogen is identified as the Bacillus strain used in the ELDER study product) will be classed as a SAR. In such cases, the trial staff should complete a purpose-designed SAR form, and the original

form returned to CTC within four days of the trial staff becoming aware of these events. The trial staff completing the report should include a detailed explanation of the event and supplement the report with clinical test results; if the hospital reports are not available at the time of reporting, the trial staff should forward the follow-up information as soon as possible to CTC, who would include these additional data in the appropriate report. Related and unexpected SAEs (i.e., all unexpected SARs) will be reported to the REC within 15 days of the CI/CTC becoming aware of the event. The CTC is responsible for additionally reporting SARs to the monitoring committee and the study product manufacturer (SACCO Systems) as appropriate.

Contact details for reporting SARs
Please Email to [contact], attention Clinical Trial Coordinator
Queries
[contact] (Mon to Fri 09.00 – 17.00)

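### The only product-harm stop criterion in section 9.2 is garbled and, as printed, is not met by a single confirmed serious adverse reaction

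*Protocol*

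**What the plan says.** Section 9.2 of the protocol gives three events, apart from a resident's own choice, that end the intervention for that resident: a positive CV-19 test; "Prolonged hospitalisation for any medical or surgical reasons not otherwise diagnosed at the time of recruitment"; and "Experiences in unexpected series of adverse reactions to the study product". Only the third concerns harm from the product.

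The safety sections use a defined term for serious product harm. Section 10.1 states that "an SAE thought to be probably or certainly related to the study product will be referred to as a Serious Adverse Reaction (SAR". Section 10.5.3 repeats the definition and sets out what follows: the delivery staff and coordinator classify the event, the chief investigator confirms it, and a SAR form is completed, with the "form returned to CTC within four days of the trial staff becoming aware of these events". It adds that "Related and unexpected SAEs (i.e., all unexpected SARs) will be reported to the REC within 15 days". The front matter on SAR reporting says that "the Clinical Trial Coordinator should be informed immediately, and a SAR form should be completed by the responsible person".

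On dosing, section 8 says "All subjects will be asked to drink a glass of plain/supplemented milk once daily, five days a week, for nine months", and that "Participants admitted to the hospital would not be expected to continue taking the study product during their hospital stay".

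**The concern.** The bullet does not parse as English, does not use the protocol's own term, and gives no number, severity or time window for a series. Taken literally, it asks for more than one reaction before the product must be stopped. The safety sections treat one related serious event as enough to set off classification, confirmation and expedited reporting. So the rule that ends exposure has a different, and apparently higher, threshold than the rule that starts reporting.

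At stake is an operative participant-safety instruction. The product is given by the resident's routine caregiver, and probiotic sachets are delivered to the home at the start. Site staff need a plain rule on when to stop and whether to restart. As the bullet stands, they have no express instruction after a first confirmed SAR that does not lead to a prolonged admission.

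**Working it through.** No arithmetic applies. The check sets the stop list in 9.2 against the other sections that could supply a stop rule.

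**1. Is the wording likely to be a slip?** Section 10.5.3 speaks of unexpected SARs, and section 10.3.2 says that the listed gastrointestinal symptoms become unexpected if they reach the SAR definition. *An unexpected serious adverse reaction* is therefore the phrase that fits the rest of the document. The abbreviation list also expands SAR as serious adverse event, so the terminology slips elsewhere too. A fault in reading the PDF is unlikely, because the printed words are intact and the noun is plural. The intended wording remains an inference. The smallest grammatical repair, *an unexpected series of adverse reactions*, would still miss a single SAR.

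**2. Which cases does each reading catch?**

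| Case | 9.2 bullet as printed | Bullet read as an unexpected SAR | Other visible text |
|---|---|---|---|
| One SAR, prolonged admission for a condition not diagnosed at recruitment | Not met | Met if unexpected | Second trigger in 9.2 ends the intervention |
| One SAR, short admission | Not met | Met if unexpected | Section 8 pauses product during the stay; silent on restarting |
| One SAR, no admission (serious for another reason listed in 10.1, such as disability or medical significance) | Not met | Met if unexpected | No express stop |
| Repeated unexpected non-serious reactions | Met | Not met | No express stop |

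The second and third rows are the gap under the printed wording. The fourth shows that simply swapping in the likely intended phrase would open a different gap.

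**3. Does any other section close the gap?**

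- Section 10.5.3 gives confirmation, form and reporting steps for a SAR, and no dosing instruction.
- Sections 15.4 and 15.5 let the steering committee and the data monitoring committee (DMC) consider changing the protocol or ending the study. They also provide for emergency meetings and urgent contact with the DMC when a resident's safety is at risk. These are escalation routes. None states that product stops for the resident concerned.
- Section 20 shows what an express rule looks like: for CV-19 it tells sites in plain terms to stop the intervention at once. Nothing equivalent is written for a SAR.
- The SAE safety reporting flowchart, and a figure at the end of section 10.5.2, are not shown in the text available. Either could contain a stop step.

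**The case against.** The strongest reply is that nothing is missing once the slip is read as intended. Section 10.3.1 expects no adverse events on the manufacturer's information, and 10.3.2 makes the listed symptoms unexpected once they are SARs. Essentially every SAR would then be unexpected, and 9.2 would already stop product after one. This supports treating the point as a correction of wording. It does not remove the point, because a site has only the printed line, and that line does not say this.

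The reply also narrows the practical gap, and this stands. The examples of a SAR in 10.5.3 are confirmed septicaemia or isolation of the product strain. Such a resident would usually be in hospital, where product is paused, and a prolonged stay is itself a trigger. Care homes do not confirm SARs: by the time one is confirmed, the coordinator and chief investigator know of it. The immediate notice in the front matter and the urgent DMC contact in 15.5 make advice to stop likely. Against that, the immediate notice applies to an event already meeting the SAR definition, while sections 10.5.1 and 10.5.2 allow events to reach trial staff at a monthly visit.

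A reader might infer two stronger things. One is that the protocol would keep a resident on product after a confirmed SAR. The documents do not support this: the protocol does not direct continuation, the resident may withdraw at any time, the escalation routes exist, and the flowchart cannot be read. The other is that extra exposure could be sized from the four-day deadline for the form or the 15-day deadline for the ethics committee. Those are reporting deadlines. They do not govern when dosing ends, so glasses counted within them would be neither an estimate nor an upper limit of exposure caused by the wording.

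**Conclusion.** The point holds as a minor one. The product-harm bullet in 9.2 is garbled, and as printed a single confirmed SAR does not trigger it. No visible text expressly stops product after one SAR without prolonged hospitalisation. The residual gap is a SAR with a short admission or none.

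Few residents are likely to be affected. The protocol gives no SAR rate and expects only minor reactions, so no number can be attached. No sample size, estimate or analysis changes.

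The conclusion that the line is garbled rests on the text alone and is firm. The conclusion that no stop step exists is limited to the visible text and would fall if the flowchart contains one. Even then the bullet should be corrected to agree with it. That the authors meant *an unexpected serious adverse reaction* is a probable reading, not an established one.

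**What to change.** Reword the third bullet in 9.2 so that it keeps both triggers, for example: *Experiences a serious adverse reaction (SAR, section 10.5.3), or repeated unexpected adverse reactions, to the study product.* A SAR-only replacement should be avoided, because it would delete the only printed trigger for repeated non-serious reactions, such as persistent gastrointestinal symptoms in a frail resident.

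Add one sentence to 10.5.3: study product is stopped for that participant when a SAR is suspected, and is permanently discontinued once the SAR is confirmed. Check that the flowchart says the same.

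The cost is one line and one sentence. The downside is possibly a few more discontinuations of study product.

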#### 10. Safety Assessment

#### 10.1 General Definition

# Adverse Event (AE)

Any untoward medical occurrence in a clinical trial subject which does not necessarily have a causal relationship with this treatment [Dir 2001/20/EC Art 2(m)]. An adverse event can therefore be any unfavourable and unintended sign (including an abnormal laboratory finding), symptom, or disease (ICH-E2D Guideline).

# Serious Adverse Event (SAE)

In research other than CTIMPS, an SAE is any adverse event that a) Results in death; (b) Is life-threatening\*; (c) Requires hospitalisation or prolongation of existing hospitalisation; (d) Results in persistent or significant disability or incapacity; (e) Consists of a congenital anomaly or birth defect or (f) Is otherwise considered medically significant by the investigator. [The Medicine for Human Use (Clinical Trials) Regulations (2004) as amended; and the Dir 2001/20/EC Art 2(o)]

\*Life-threatening in this context refers to a reaction in which the patient was at risk of death at the time of the reaction; it does not refer to a reaction that hypothetically might have caused death if more severe (ICH-E2D Guideline).

An SAE occurring to a research participant should be reported to the REC where in the opinion of the CI, the event was:

- ➤ Related that is, it resulted from the administration of any of the research procedures, and
- ➤ Unexpected that is, the type of event is not listed in the protocol as an expected occurrence.

Therefore, the relatedness or unexpectedness of an event will be reviewed by the CI at each site and wherein the opinion of the CI, the SAE will be classed appropriately and reported to the main REC. For ease of recording and reporting, in this study, an SAE thought to be probably or certainly related to the study product will be referred to as a Serious Adverse Reaction (SAR).

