# 10.2 Causality

This study uses the following instruction to assign causality to report SAE (31)

| Relationship   | Description  |
|----------------|--|
| Unrelated      | No evidence of any causal relationship between the AE and the trial                  |
|                | medication/study intervention  |
| Unlikely       | Little evidence to suggest there is a causal relationship (e.g., the event did not   |
|                | occur within a reasonable time after administration of the study product) or there   |
|                | is another reasonable explanation for the event (e.g., the participant's clinical    |
|                | condition or other treatment).   |
| Possible       | There is some evidence to suggest a causal relationship with the study product       |
|                | (e.g., because the event occurs within a reasonable time after administration of the |
|                | study product), but the influence of other factors may have also contributed to the  |
|                | event (e.g., the participant's clinical condition or other treatments).              |
| Probable       | There is evidence to suggest a causal relationship with the study product and that   |
|                | the influence of other factors is unlikely.  |
| Definite       | There is clear evidence to suggest a causal relationship with the study product and  |
|                | that other possible contributing factors can be ruled out.                           |
| Not Assessable | There is insufficient/incomplete evidence to make a clinical judgment of a causal    |
|                | relationship   |

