# 10.4 Reporting Period

The adverse event reporting period for this study begins as soon as the resident provides informed consent and ends one month after the final data collection. The study products (probiotics and fluoridated milk) being used in this trial is a well-established food supplement, and given the frailty of the study population with a wide range of healthcare needs, it's critical not to cloud any true emerging safety signals by collecting unrelated data. Therefore, safety reporting in this study will focus on SAEs that could be related to the study population, and only SARs that could be related to the study product will be assessed for expectedness. The onset of any AE will be apparent particularly to care home staff, as they know their residents and their medical conditions thoroughly and so can quickly identify any deterioration to a resident's health very early. The care home staff will be informed of the pre-specified events that could be expected with the study.

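### Section 10.1 makes unexpected SAEs from any research procedure reportable to the REC, but the causality scale, expectedness step and 15-day report are worded for the study product only

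*Protocol*

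**What the plan says.** Section 10.1, under the SAE definition, sets the rule for the ethics committee: "An SAE occurring to a research participant should be reported to the REC where in the opinion of the CI, the event was" both related and unexpected. Related is explained as meaning that "it resulted from the administration of any of the research procedures". The CI is to review relatedness and unexpectedness, after which "the SAE will be classed appropriately and reported to the main REC". The same section then introduces a narrower label: "an SAE thought to be probably or certainly related to the study product will be referred to as a Serious Adverse Reaction (SAR".

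The later sections work with the narrower idea:

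- **10.2 Causality.** The category for a possible link reads "There is some evidence to suggest a causal relationship with the study product". The probable and definite categories also name the study product.
- **10.4 Reporting Period.** The reporting period "begins as soon as the resident provides informed consent", but "only SARs that could be related to the study product will be assessed for expectedness".
- **10.5.3 Serious Adverse Reaction.** "Related and unexpected SAEs (i.e., all unexpected SARs) will be reported to the REC within 15 days" of the CI or CTC becoming aware of the event.

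Section 9.1 lists what is done to residents apart from giving milk: a visual and tactile oral examination, swabs of the buccal mucosa and the floor of the mouth, stimulated saliva from willing participants, and optional plaque sampling with an interdental brush. These take place at baseline and at nine months.

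**The concern.** Section 10.5.3 presents two sets as identical when they are not. The set defined in 10.1 contains unexpected SAEs related to the product or to any other research procedure. The set of unexpected SARs contains only those related to the product. The 15-day deadline is attached to the smaller set.

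Staff who follow 10.2, 10.4 and 10.5.3 as written would therefore leave out events that 10.1 requires to be reported. The participants are care home residents aged 65 or over, whom the protocol itself describes as frail. At stake is whether serious harm from an examination or a sample would be classified and would reach the REC on a defined timescale. It also matters whether the causality scale could record such harm as related at all.

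**Working it through.** No alpha, power or sample-size calculation is involved. The check takes one hypothetical event, a serious and unexpected SAE caused by the oral examination or by sampling, and follows it through the protocol.

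| Step | Section | Wording applies to | Result for this event |
|---|---|---|---|
| REC rule | 10.1 | any research procedure, with CI review | reportable |
| SAE collection | 10.5.2 | all SAEs, monthly, from consent | collected, with a second assessor |
| Causality grade | 10.2 | possible, probable and definite name the study product | no graded category fits |
| SAR label | 10.1, 10.5.3 | probable or certain/definite relation to the study product | not a SAR |
| SAR form within four days | 10.5.3 | SARs | not triggered |
| Expectedness | 10.4 | SARs that could be product-related | not assessed under this section |
| 15-day REC report | 10.5.3 | unexpected SARs | no deadline applies |

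The event is reportable at the first step and drops out of the classification and timing steps. Section 10.1 asks for a judgement of unexpectedness on this event and 10.4 restricts that judgement to SARs, so the two sections conflict directly.

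**Baseline visit.** Section 10.4 starts safety reporting at consent. Section 6.4 reveals the allocation only after baseline data collection, and section 8 distributes product after allocation. An SAE that occurs at the baseline examination therefore falls inside the reporting period but before any exposure to product. It cannot be product-related and so cannot be a SAR, although 10.1 may make it reportable.

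**Planned exposure.** The inputs are 240 participants (section 11.1) and two examination visits each (section 9.1).

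- All visits: 240 × 2 = 480.
- Visits before any product: 240 × 1 = 240.

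Both are upper limits that assume full recruitment, and the 480 also assumes no loss over nine months. The visits are not uniform: stimulated saliva and plaque are optional, and edentulous participants provide saliva samples only. The counts show how many visits the wording affects. They say nothing about how often a serious event would occur.

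**The case against.** A reader might infer that serious harm from examination or sampling has no route to the ethics committee. The protocol does not support that. The words about research procedures are themselves part of a REC reporting rule, the rule includes CI review, and it does not depend on the SAR label, which 10.1 introduces afterwards as a convenience for recording and reporting.

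Nor is every later step limited to the product. Section 10.5.2 collects all SAEs from consent, uses a second assessor, and has the CI confirm the grade when the assessors differ. Section 15.5 lets the DMC review AE data and ask for further analysis. The SAE reporting flowchart could not be read in the text available, so nothing can be said about what it adds. It also does not follow that the safety results would show no procedure-related events whatever happened, because SAEs are recorded with free-text comments and come under the CI's any-procedure test.

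These points stand and they limit the finding. They do not remove it. Section 10.1 gives no timescale, and the grading and expectedness work that would inform the CI's judgement is worded for the product. The SAE form in 10.5.2 is named as a safety report to the REC, but 10.5.1 uses the same form name for ordinary AEs, so the name cannot mean that each completed form is sent to the REC.

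It is also fair to say that the documents give no example or rate of a serious event from a swab, an interdental brush or a tactile examination. Such events may be rare.

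**Conclusion.** The protocol contradicts itself. Section 10.1 requires REC reporting of unexpected SAEs related to any research procedure. Sections 10.2, 10.4 and 10.5.3 word graded causality, expectedness and the 15-day report for the study product only, and the equation of the two sets in 10.5.3 is wrong. Procedure-related SAEs have a general rule but no matching causality category, expectedness step or deadline.

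This is an inconsistency in safety reporting. It changes no sample size, estimate or test. Up to 480 planned visits are affected, 240 of them before any product, and the expected number of events cannot be derived from the documents. The conclusion rests on the text of section 10 as it can be read, without the flowchart. It should be corrected because the protocol's own reporting duty is at issue and the change is small.

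**What to change.** Bring the later sections into line with 10.1:

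1. **10.5.3:** delete or correct the parenthesis that equates related and unexpected SAEs with unexpected SARs, so that the 15-day REC report covers every unexpected SAE related to the study product or to any research procedure.
2. **10.4:** extend the sentence on expectedness to the same set.
3. **10.2 and the SAE form:** word the causality categories to include a relation to research procedures, and add a field to record it.
4. **Flowchart:** check that it agrees with the revised text.

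Keep the SAR label for product-related events. Widening it to cover procedures would bring examination and swab events under the provision in 10.5.3 for reporting SARs to the product manufacturer, which serves no purpose here.

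The cost is wording in three sections, one form field and slightly more assessment work for the delivery staff, the CTC and the CI.

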# 15.5 Data Monitoring Committee

The Data Monitoring Committee (DMC) will be established to oversee the safety and design of the study. The members of the DMC are a small group of three members – two members from the coinvestigator team and a third member who would be completely independent of the trial. The rationale not to have a mixed DMC and rather have all independent members is that the ELDER STUDY is a

feasibility trial, and the primary objective is to refine the overall structure and procedure for a definitive trial.

As highlighted in the above session, the DMC takes up an advisory role to the SSC and offers recommendations on all matters relating to patient safety and reporting. Therefore, the committee will take responsibility for reviewing safety data reporting of AEs and line-listings of reported SARs captured throughout the trial and, if the need arises, request further analysis. Furthermore, apart from monitoring for safety signals, the DMC will also be asked to a) advise on whether the data collected is valid by verifying for completeness and accuracy; b) assesses the accumulated data for scientific merit to justify the continuing recruitment of further participants; and finally, c) monitor if clinical equipoise was maintained throughout the duration of the study.

The DMC will be asked to convene at least twice a year and provide advice to the SSC. In case of safety issues, an emergency meeting will be called for. The Coordinating Centre will be in constant communication by emails and telephone with DMC to seek advice on urgent matters, such as when a participant's safety is threatened.

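### SAEs rated possibly related fall outside the SAR definition, and section 10.5.3 ties 15-day ethics committee reporting to SARs, which is narrower than the protocol's own rule in 10.1

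*Protocol*

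**What the plan says.** - **Protocol 10.1 (SAE definition).** An SAE goes to the REC if, in the CI's opinion, it meets two conditions. The first is "Related that is, it resulted from the administration of any of the research procedures"; the second is that this type of event is not listed in the protocol as expected. No causality category is named. The section then adds a label: "an SAE thought to be probably or certainly related to the study product will be referred to as a Serious Adverse Reaction (SAR").
- **Protocol 10.2 (causality table).** *Possible* is a level of its own: "There is some evidence to suggest a causal relationship with the study product", with other factors perhaps contributing. *Probable* needs those other factors to be unlikely.
- **Protocol 10.3.2.** Minor gastrointestinal symptoms are expected events. They become unexpected if they meet the SAR definition.
- **Protocol 10.4.** On expectedness, "only SARs that could be related to the study product will be assessed for expectedness".
- **Protocol 10.5.2.** All SAEs are collected monthly. Two assessors rate causality on five levels, *possibly* among them. If they differ, the higher rating is taken and the CI confirms it.
- **Protocol 10.5.3.** A SAR is "An SAE classified by the delivery staff/CTC and further confirmed by the CI as being probably or definitely related to the study product", followed by a parenthesis on "diagnostic tests confirming septicaemia or the suspected pathogen is identified as the Bacillus strain used in the ELDER study product". The reporting rule is: "Related and unexpected SAEs (i.e., all unexpected SARs) will be reported to the REC within 15 days".
- **Protocol 15.5.** The DMC reviews AE safety data and "line-listings of reported SARs".

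**The concern.** A SAR threshold set at *Probable* would matter little if SAR were only a label. In this protocol SAR status switches on nearly every fast safety action, so where the threshold sits decides which events are looked at promptly. Section 10.5.3 also appears to shrink the REC obligation that 10.1 lays down, by equating related SAEs with SARs.

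The population adds weight. Sections 10.3 and 10.6 expect residents to have comorbidities and many background health events. Competing explanations are what separates *Possible* from *Probable* in 10.2, so a real signal could well sit at *Possible*. At stake is how soon the REC, the manufacturer and the DMC learn of serious events for which there is some evidence that the product contributed.

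**Working it through.** No figure in the protocol needs reproducing. The check sets the rules side by side.

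**1. Where the threshold lies.** The ordered scale in 10.2 is unrelated, unlikely, possible, probable, definite, with *Not Assessable* apart. Both SAR definitions (10.1 and 10.5.3) start at probable. An SAE finally rated *Possible* is not a SAR under either.

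**2. What each route depends on.**

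| Route | Trigger | SAE finally rated *Possible* |
|---|---|---|
| Immediate notice to the coordinator (SAR reporting note at the front) and SAR form within four days (10.5.3) | SAR | No |
| Expectedness assessment (10.4) | SAR | No |
| REC report within 15 days (10.5.3) | Unexpected SAR | No |
| Reports to the monitoring committee and manufacturer (10.5.3) | SAR | No |
| DMC line-listing (15.5) | SAR | No |
| REC report under the general rule (10.1) | CI considers it related and unexpected | Open, see step 3 |
| Monthly collection and two-assessor rating (10.5.2) | Any SAE not excluded by 10.6 | Yes |
| DMC review of AE data (15.5) | AE | Yes |

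**3. Does the general rule in 10.1 rescue these events?** It needs both related and unexpected. The CI may call a *Possible* event related, since 10.1 has no cut-off. But 10.4 provides for expectedness assessment only of SARs, so no procedure supplies the second condition. For the gastrointestinal events in 10.3.2 the text goes further. A hospitalisation for such symptoms rated *Possible* is an SAE but not a SAR, so it stays expected and fails the 10.1 test as well. For other event types the CI could still compare the event with the protocol's list and report it, but 10.5.3 states the narrower rule.

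**4. Does the higher-rating rule help?** It moves an event up only when the assessors differ. If both say *Possible*, the result is *Possible*.

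**5. How many events?** The protocol gives no distribution of ratings. For illustration only, let q be the assumed chance that one assessor rates a suspected SAE *Possible* rather than *Probable* or *Definite*. If the assessors always agree, the share left out is q. If they rate independently and the higher rating stands, it is q × q.

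| q (assumed) | Independent, q² | Full agreement, q |
|---|---|---|
| 0.5 | 25% | 50% |
| 0.7 | 49% | 70% |
| 0.8 | 64% | 80% |
| 0.9 | 81% | 90% |

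More than half are left out only if q exceeds 0.50 (full agreement) or √0.5 ≈ 0.71 (independence). Nothing in the protocol says where q lies.

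**The case against.** The threshold can be defended as a deliberate choice. Section 10.4 explains that the products are established food supplements, that residents are frail, and that collecting unrelated events could hide a true signal. The protocol treats the study as a non-CTIMP, and none of its passages requires possibly related events to count as reactions. The criterion in 10.1 that the event resulted from a research procedure arguably lies nearer to probable than to possible, and it leaves the decision to the CI. The wording in 10.4 about SARs that could be related may be loose drafting rather than a second definition. Oversight is not absent: all SAEs are collected monthly, a second assessor and the CI look at causality, and the DMC sees AE data and may ask for more analysis.

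Much of this stands. The 10.4 wording is weak support and the point does not rest on it. Monthly collection and DMC review of AE data are real safeguards. What they do not supply is an expedited route. The CI's discretion still needs a finding of unexpectedness that 10.4 reserves for SARs. The SAE form is named as a safety report to the REC, but 10.5.1 uses the same form for ordinary AEs, so its name does not show that each one is sent.

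A reader might infer that most suspected reactions would never reach the REC. The protocol does not support that. *Most* needs a distribution of ratings that it does not give. *Probable* asks that other factors be unlikely for the event in hand, not that the resident be free of comorbidity, and 10.6 removes many of the most confounded events before any rating. *Never* ignores the discretion in 10.1.

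**Conclusion.** The point holds as a conflict between safety rules that the protocol itself fixes. Sections 10.1 and 10.5.3 leave *Possible* out of the SAR definition, and the reporting sentence in 10.5.3 makes that exclusion operative by limiting the 15-day REC report to unexpected SARs. This is narrower than the general rule in 10.1. Together with 10.3.2 and 10.4 it leaves a possibly related SAE without a stated expedited route to the REC or the manufacturer, or a place in the DMC's SAR line-listings.

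The effect is on speed and certainty of review; such events are still recorded and do not escape all oversight. Its size in events cannot be given. The conclusion rests on reading 10.5.3 literally, as equating related SAEs with SARs, and on the final rating being *Possible* after the two-assessor step and CI confirmation.

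**What to change.** Reconcile 10.1, 10.3.2, 10.4 and 10.5.3:

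- In 10.1 and 10.5.3, define a SAR as an SAE rated possibly, probably or definitely related to the study product, using the category names of 10.2. Mark the parenthesis on diagnostic tests in 10.5.3 as an example, so that it cannot be read as a further condition.
- With that definition, 10.4 brings such SAEs into expectedness assessment, 10.5.3 sends the unexpected ones to the REC, and 15.5 puts them in the DMC line-listings. Check that 10.3.2 reads correctly under the wider definition, and reword the clause in 10.4 on SARs that could be related, which would then be redundant.
- State what happens to an SAE rated *Not Assessable*. That category is in the 10.2 table but missing from the assessors' list in 10.5.2.

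The cost is a few reworded sentences, plus some additional SAR forms and REC reports. Their number cannot be estimated from the protocol.
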